- P:** Patient diary is to be completed (at the study site or home) at any time between infusion and next study visit. IgPro20 infusion form to be completed by study personnel or nurse only, immediately after infusion.
- Q:** Adverse events and concomitant therapy will not be recorded at site or home visits if PK sample collection is the only scheduled activity.

Pharmacokinetic Schedule of Assessments: Sequence A**Treatment Period 1**

Week	1	5	9	13	14						15
PK Timepoint ^D	Baseline (1 to 60 min before 1 st infusion)	Trough (1 to 60 min before 1 st infusion)	Trough (1 to 60 min before 1 st infusion)	Trough (1 to 60 min before 1 st infusion)	Trough (1 to 60 min before 1 st infusion of Week 14) ^A	24 h (1 d) ± 4 h (after 1 st infusion, Week 14)	48 h (2 d) ± 6 h (after 1 st infusion, Week 14)	72 h (3 d) ± 6 h (after the 1 st infusion, Week 14)	96 h (4 d) ± 6 h (after 1 st infusion, Week 14)	168 h (7 d) ± 10 h (after 1 st infusion, Week 14)	240 h (10 d) ± 10 h (after 1 st infusion, Week 14)
PK sample collection	AH1 ^B	AH2 ^B	AH3 ^B	AH4 ^B	AH5 ^C	AH6 ^C	AH7 ^C	AH8 ^C	AH9 ^C	AH10 ^{C,D}	AH11 ^C

AH = Treatment Period 1 IgPro20; d = days; min = minutes; PK = Pharmacokinetic.

Treatment Period 2

Week	17	21	25	29			30		31	32	
PK Timepoint ^D	(1 to 60 min before 1 st infusion)	Trough (1 to 60 min before 1 st infusion)	Trough (1 to 60 min before 1 st infusion)	Trough (1 to 60 min before 1 st infusion)	Immediately after the end of 1 st infusion, Week 29 (1 to 60 min) ^A	1 to 60 min after 2 nd infusion, Week 29	168 h (7d) ± 6 h (after 1 st infusion, Week 29)	264 h (11d) ± 10 h (after 1 st infusion, Week 29)	336 h (14d) ± 10 h (after 1 st infusion, Week 29)	504 h (21 d) ± 24 h (after 1 st infusion, Week 29)	672 h (28d) ± 24 h (after 1 st infusion, Week 29)
PK sample collection	AP12 ^B	AP13 ^B	AP14 ^B	AP15 ^B	AP16 ^B	AP17 ^B	AP18 ^{C,D}	AP19 ^C	AP20 ^{C,D}	AP21 ^{C,D}	AP22 ^{B,D}

AP = Treatment Period 2 IgPro10; d = days; min = minutes; PK = pharmacokinetic.

A: Serves as the reference collection for the subsequent follow-up collections.

B: Sample collected at a site visit.

C: Sample collected at a home visit.

D: Sample should be collected at the hour of timepoint (± window) indicated, even if not aligned with indicated week.

Pharmacokinetic Schedule of Assessments: Sequence B**Treatment Period 1**

Week	1	5	9	13				14		15	16

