PK Timepoint ^E	Baseline (1 to 60 min before 1 st infusion)	Trough (1 to 60 min before 1 st infusion)	Trough (1 to 60 min before 1 st infusion)	Trough (1 to 60 min before 1 st infusion)	Immediately after the end of 1 st infusion, Week 13 (1 to 60 min) ^A	1 to 60 min after 2 nd infusion, Week 13	168 h ± 6 h (7d) (after 1 st infusion, Week 13)	264 h (11 d) ± 10 h (after 1 st infusion, Week 13)	336 h (14 d) ± 10 h (after the 1 st infusion, Week 13)	504 h (21 d) ± 24 h (after the 1 st infusion, Week 13)	672 h (28 d) ± 24 h (after 1 st infusion, Week 13)
PK sample collection	BP1 ^B	BP2 ^B	BP3 ^B	BP4 ^B	BP5 ^B	BP6 ^B	BP7 ^{C,E}	BP8 ^C	BP9 ^{C,E}	BP10 ^{B,E}	BP11 ^{D,E}

BP = Treatment Period 1 IgPro10; d = days; min = minutes; PK = Pharmacokinetic.

Treatment Period 2

Week	17	21	25	29	30						31
PK Timepoint ^E	1 to 60 min before 1 st infusion	Trough (1 to 60 min before 1 st infusion)	Trough (1 to 60 min before 1 st infusion)	Trough (1 to 60 min before 1 st infusion)	Trough (1 to 60 min before 1 st infusion, Week 30) ^A	24 h (1 d) ± 4 h (after 1 st infusion, Week 30)	48 h (2 d) ± 6 h (after 1 st infusion, Week 30)	72 h (3 d) ± 6 h (after 1 st infusion, Week 30)	96 h (4 d) ± 6 h (after 1 st infusion, Week 30)	168 h (7 d) ± 10 h (after 1 st infusion, Week 30)	240 h (10 d) ± 10 h (after 1 st infusion, Week 30)
PK sample collection	BH12 ^{B,D}	BH13 ^B	BH14 ^B	BH15 ^B	BH16 ^C	BH17 ^C	BH18 ^C	BH19 ^C	BH20 ^C	BH21 ^{C,E}	BH22 ^C

BH = Treatment Period 2 IgPro20; d = days; min = minutes; PK = Pharmacokinetic.

A: Serves as the reference collection for the subsequent follow-up collections.

B: Sample collected at a site visit.

C: Sample collected at a home visit.

D: BP11 and BH12 can be taken at the same time point, if appropriate with dosing schedule and visit window.

E: Sample should be collected at the hour of timepoint (± window) indicated, even if not aligned with indicated week.

Table of Contents

Clinical Study Protocol Synopsis	5
Schedule of Assessments: Sequence A, Treatment Period 1 (IgPro20).....	10
Schedule of Assessments: Sequence A, Treatment Period 2 (IgPro10).....	13
Schedule of Assessments: Sequence B, Treatment Period 1 (IgPro10).....	15
Schedule of Assessments: Sequence B, Treatment Period 2 (IgPro20).....	18
Pharmacokinetic Schedule of Assessments: Sequence A	21
Pharmacokinetic Schedule of Assessments: Sequence B	22
Table of Contents	23
List of Tables.....	30
List of Figures.....	30
List of Abbreviations	31
1 Introduction	36
1.1 Background	36

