2.2.2 Secondary Endpoints

Secondary Objective	Endpoint	Summary Measure(s) (To be determined at the end of each treatment period [Period 1, Week 16; Period 2, Week 32; combination of treatment, Week 32])
1	IgPro20 relative bioavailability (%F)	Geometric mean ratio of area under the serum IgG concentration time curves within a dosing duration (dose-normalized area under the curve to the end of the dosing period [AUC _{0-tau}]) following administration of the first dose of IgPro20 or IgPro10 in the last week of dosing for Sequence A and / or Sequence B
2	IgPro20 PK parameters (AUC _{0-tau} , area under the curve to the last dosing period [AUC _{0-last}], maximum [peak] plasma drug concentration [C _{max}], minimum plasma drug concentration [C _{trough}])	Geometric mean of PK parameters and corresponding 95% confidence interval (CI) by treatment in each sequence
3	IgPro10 PK parameters (AUC _{0-tau} , AUC _{0-last} , C _{max} , C _{trough})	Geometric mean of PK parameters and corresponding 95% CI by treatment in each sequence
4	The safety of IgPro10 based on AEs, including any AEs, TEAEs, SAEs, and AESIs	AEs measured by treatment, treatment sequence, combination of treatment and treatment period: 
 • Number and percentage of subjects with AEs, TEAEs, SAEs, and AESIs (total, severity, causality and outcome) • Number and percentage of subjects with categorized as ISRs (total, severity, causality and outcome)

Secondary Objective	Endpoint	Summary Measure(s)
		(To be determined at the end of each treatment period [Period 1, Week 16; Period 2, Week 32; combination of treatment, Week 32])
	The safety of IgPro10 based on the change in other clinical tests	Changes from baseline as measured by treatment, treatment sequence, combination of treatment and treatment period 
• Vital signs• Body weight• Clinical laboratory tests• ECG• PFTs

2.3

CCI [Redacted]

2.3.1

CCI [Redacted]

CCI [Redacted]

2.3.2

CCI [Redacted]

CCI [Redacted]

2.4

CCI [Redacted]

CCI [Redacted]

CCI

3 Study Overview

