3.2.2 IgPro10

Subjects will receive IgPro10 at a total dose of 2 g/kg split over 2, 3, 4, or 5 consecutive days, depending on total dose and individual tolerability, every 4 weeks. The total dose / volume of all IP will be calculated based on body weight. Changes of > 10% of body weight and the corresponding adjustment will follow the same way as IgPro20 in [Section 3.2](#).

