Subsequent infusions	
Rate of 0.3 mL/kg/h (30 mg/kg/h; 0.005 mL/kg/min; 0.5 mg/kg/min);
 
If well tolerated within 30 min: increase to 0.6 mL/kg/h (60 mg/kg/h; 0.01 mL/kg/min; 1.0 mg/kg/min) for another 30 min;
 
If well tolerated within an additional 30 min increase to 1.2 mL/kg/h (120 mg/kg/h; 0.02 mL/kg/min; 2 mg/kg/min);
 
If well tolerated within an additional 30 min increase to 2 mL/kg/h (200 mg/kg/h; .033 mL/kg/min; 3.3 mg/kg/min)
 
(An infusion rate 2 mL/kg/h is the maximum for subjects with eGFR < 90 mL/min/1.73m² at Screening and for subjects with elevated serum creatinine level as detailed in the renal safety management algorithm in Section 8.1.1.4; lower infusion rates may be administered at the discretion of the investigator).

Increases in infusion rate should be performed cautiously, as the risk of AEs in IVIG infusions generally tends to correlate with the infusion rate. Subjects with renal insufficiency should always be infused at the lowest practicable rate.

Detailed information in reference to IgPro10 administration (eg, amount of IgPro10 received, any dose adjustments, infusion rate, whether infusion was omitted, interrupted or stopped and reason, and infusion start / stop time / date) will be documented on the IgPro10 infusion form.

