LLN	Lower limit of normal
CCI	CCI
MedDRA	Medical Dictionary for Regulatory Activities
CCI	CCI
PFT	Pulmonary function test
CCI	CCI
PID	Primary immunodeficiency
PK	Pharmacokinetics
SAE	Serious adverse event
SAF	Safety analysis set
SAP	Statistical analysis plan
SC	Subcutaneous
SD	Standard deviation
CCI	CCI
SMQ	Standardized MedDRA queries
SOC	System Organ Class
SSc	Systemic sclerosis
CCI	CCI
TEAE	Treatment-emergent adverse event
TEE	Thromboembolic event
CCI	CCI
ULN	Upper limit of normal
CCI	CCI

Glossary of Terms

Term	Definition
Baseline Value	The most recent assessment before the first infusion in Treatment Period 1.
End of Study (EOS)	The follow-up telephone call occurs 4 weeks after completing study treatment or early termination follow-up visit, whichever occurs later.
End of Treatment (EOT)	End of treatment is either end of Week 32 for completed subjects or at early termination visit.
Infusion	
IgPro10 An infusion comprises all IP exposure on one day of infusion. In the IgPro10 Treatment Periods, there are 2 to 5 consecutive days of infusions and so 2 to 5 Infusions planned per 4-week period.
 
IgPro20 An infusion comprises all IP exposure on one day (one session). In the IgPro20 Treatment Periods, there are 2 sessions and so 2 infusions planned per week.

Infusion Cycle (IgPro10 only)	One Infusion Cycle consists of 2, 3, 4 or 5 consecutive days of infusions with a planned total dose of 2 g/kg IgPro10 every 4 weeks. There are 4 planned Infusion Cycles of IgPro10 per IgPro10 Treatment Period in each Treatment Sequence.
Weekly Infusions (IgPro20 only)	A Weekly Infusion consists of 2 sessions (2 Infusions) with a planned total dose of 0.5 g/kg IgPro20 per week. There are 14 Weekly Infusions of IgPro20 per IgPro20 Treatment Period per each Treatment Sequence.
Infusion Session (IgPro20 only)	One Infusion Session consists of 1 infusion day. There are 2 Infusion Sessions within each weekly infusion with a planned total dose of 0.5 g/kg IgPro20 per week.
Protocol Deviation	
All instances when either subjects who have been entered in the study and / or the study sites deviate from the IEC / IRB-approved study protocol.
 
A key protocol deviation is any protocol deviation that could have a significant effect on the subject's safety, rights, or welfare and / or on the integrity of the study data.

Reference Visit	Reference visit for Treatment Period 1 is Week 1. Reference visit for Treatment Period 2 is Week 17.

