12.2 Deriving and Summarizing Pharmacokinetic Parameters

Non-compartmental PK analysis will be performed by CSLB or its designate for PK parameter estimations using Phoenix WinNonlin, Version 6.3 or higher. Only concentrations - time profiles following the first infusion of the last infusion cycle in each Treatment Period and Treatment Sequence will be used to calculate the PK parameters. The following PK parameters will be derived using actual sampling collection times:

AUC _{0-tau}	Area Under the concentration-time Curve from time point zero to tau, calculated using a combined linear and logarithmic trapezoidal rule (linear up-log down).
AUC _{0-last}	
Area under the concentration time curve from time point zero to the last quantifiable time point, calculated by the linear up/log down rule [mass x time x volume⁻¹]. Interpolation is linear in the constant and ascending parts of the concentration-time profiles, while the interpolation is logarithmic in the descending parts as follows:
 $\text{if } C_{i+1} \geq C_i \quad \text{AUC}_{i,i+1} = \frac{(t_{i+1} - t_i) \cdot (C_i + C_{i+1})}{2}$ $\text{and if } C_{i+1} < C_i \quad \text{AUC}_{i,i+1} = \frac{(t_{i+1} - t_i) \cdot (C_{i+1} - C_i)}{\ln(C_{i+1}) - \ln(C_i)}$ 
where AUC_{i, i+1} is the area in the time span (t_{i+1} – t_i) and C_i is the concentration at time t_i. The total area AUC_{0-last} is obtained as the sum of AUC_{S_i, i+1} from all the time intervals:
 $\text{AUC}_{0-last} = \sum_{x=1}^n \text{AUC}_{(i, i+1)}$ 
x : sampling number n: last sampling number

C _{trough}	Trough concentration in serum, collected prior to the next infusion during a treatment regimen.
C _{max}	Maximum observed concentration in serum.
t _{max}	Time to reach C _{max}

The plasma PK parameters will be listed and summarized by Treatment Period in each Treatment Sequence with mean (\pm SD) and geometric mean (geometric % CV and 95% CI) for all PK parameters except t_{\max} based on the PK set. C_{trough} will be summarized by each time point by treatment in each Treatment Sequence. t_{\max} will be listed only.

Table 9: Reference time points for the calculation of PK parameters

Treatment	Parameter	Start *	End *
IgPro20	tau	168 h	
	AUC _{0-tau}	AH5 BH16	AH10 BH21
	C _{max} t _{max}	AH5 BH16	Last quantifiable time point at or before AH10/BH21
	AUC _{0-last}	AH5 BH16	Last quantifiable time point at or before AH11/BH22
IgPro10	tau	672 h	
	AUC _{0-tau}	AP15 BP4	AP22 BP11

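### The last early IgPro10 PK sample follows the 2nd infusion, so observed Cmax and tmax miss the end-of-cycle peak whenever a cycle runs 3 to 5 days

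*Protocol*

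**What the plan says.** Protocol section 3.2.2 gives each IgPro10 dose "split over 2, 3, 4, or 5 consecutive days, depending on total dose and individual tolerability, every 4 weeks". The SAP glossary counts one infusion per day, so "there are 2 to 5 consecutive days of infusions and so 2 to 5 Infusions planned per 4-week period". The 2nd infusion is therefore day 2 of the cycle, and it is the last one only in 2-day cycles.

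In the profiled cycle, the Pharmacokinetic Schedules of Assessments place samples as follows:
- before the 1st infusion (AP15/BP4);
- just after the 1st infusion (AP16/BP5);
- "1 to 60 min after 2 nd infusion, Week 29" for AP17, and "1 to 60 min after 2 nd infusion, Week 13" for BP6;
- then at 168, 264, 336, 504 and 672 h after the 1st infusion.

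The visit descriptions (protocol 8.6.4.3 and 8.6.5.3) only refer back to these tables.

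SAP section 12.2 restricts the calculation to the profile after the first infusion of the last cycle, which "in each Treatment Period and Treatment Sequence will be used to calculate the PK parameters". It defines Cmax as "Maximum observed concentration in serum". Protocol section 2.2.2 names IgPro10 Cmax as a secondary endpoint, summarized as "Geometric mean of PK parameters and corresponding 95% CI by treatment in each sequence".

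**The concern.** IgG peaks at about the end of the last infusion of a cycle. In a 2-day cycle AP17/BP6 catches that peak. In a 3-, 4- or 5-day cycle the sample comes before dosing is complete, and nothing more is drawn until day 7. The observed maximum is then either a mid-dosing value or a day-7 value.

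The pooled geometric mean of Cmax would combine captured and missed peaks. It would be biased low by an amount that depends on how many days subjects happened to use. Number of days is not random: it depends on total dose and tolerability. With about 10 evaluable subjects per sequence, a different mix of cycle lengths could by itself separate the two sequence means. The confidence interval would not reflect this. The listed tmax would be wrong in the same subjects.

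**Working it through.** The plan states no figure for this point, so there is none to reproduce. The timeline uses the documents' schedule, dose and rates plus the stated dosing-pattern assumptions; the size of the Cmax error also needs assumed PK values.

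**1. Dose given when AP17/BP6 is drawn.** Inputs: 2 g/kg per cycle, one infusion per day, n = 2 to 5 days. Assumptions: even split, infusions started 24 h apart.

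- Share given = 2/n. Dose left = 2 g/kg × (1 − 2/n).
- Last infusion starts at 24(n − 1) h.
- Session length: the cycle volume is 2 g/kg ÷ 0.1 g/mL = 20 mL/kg, so 20/n mL/kg per session. The slower case follows the renal-dysfunction steps in protocol 5.1.3 ("An infusion rate 2 mL/kg/h is the maximum for subjects with eGFR" below 90). Three 30-minute steps at 0.3, 0.6 and 1.2 mL/kg/h deliver 1.05 mL/kg in 1.5 h; the rest runs at 2 mL/kg/h. For n = 3: 1.5 + (6.67 − 1.05)/2 = 4.3 h. The faster case goes up to 4.8 mL/kg/h, with assumed 30-minute steps at 0.3, 0.6, 1.2 and 2.4. For n = 3: 2 + (6.67 − 2.25)/4.8 = 2.9 h.

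| Days | Share given at AP17/BP6 | Left to give (g/kg) | Session (h) | Last infusion ends (h) |
|---|---|---|---|---|
| 2 | 100% | 0 | 3.6-6.0 | 28-30 |
| 3 | 67% | 0.67 | 2.9-4.3 | 51-52 |
| 4 | 50% | 1.0 | 2.6-3.5 | 75 |
| 5 | 40% | 1.2 | 2.4-3.0 | 98-99 |

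In 3- to 5-day cycles AP17/BP6 falls at about 28 h and the next sample at 168 h. The end of dosing lies inside that gap every time.

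**2. Size of the Cmax shortfall.** Four 28-day cycles were simulated. The fourth was sampled at 0 h, 0.5 h after infusions 1 and 2, and at 168, 264, 336, 504 and 672 h; observed and true maxima were compared. Assumed values, none in the documents: central volume 0.04-0.08 L/kg, terminal half-life 15-35 days, endogenous IgG 6-12 g/L, one- and two-compartment models (148 parameter sets).

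| Days | Shortfall, even split: 5th-95th percentile (full range) | Front-loaded split |
|---|---|---|
| 2 | under 1% | – |
| 3 | 11-19% (7-22%) | 0-11% (40/40/20) |
| 4 | 9-27% (6-31%) | 6-21% (30/30/20/20) |
| 5 | 7-26% (4-31%) | 4-25% (25/25/20/15/15) |

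The shortfall does not rise steadily with days, because the 168 h sample can become the observed maximum. Observed tmax is up to 72 h too early or 117 h too late.

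One two-compartment case as illustration (V1 40 mL/kg, V2 30 mL/kg, terminal half-life 28 days, distribution half-life 1.5 days, 4 h infusions, endogenous IgG 10 g/L):

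| Days | True Cmax (g/L), time | Observed Cmax (g/L), time | Ratio |
|---|---|---|---|
| 2 | 76.9 at 28 h | 76.7 at 28.5 h | 0.997 |
| 3 | 73.1 at 52 h | 62.2 at 28.5 h | 0.851 |
| 4 | 70.1 at 76 h | 55.1 at 28.5 h | 0.787 |
| 5 | 67.6 at 100 h | 56.2 at 168 h | 0.832 |

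A separate two-compartment run over 72 assumed parameter sets with an even split gave ratios of 0.995-0.999, 0.79-0.88, 0.70-0.89 and 0.73-0.92 for 2, 3, 4 and 5 days.

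**3. Effect on the pooled geometric mean.** If a share p of subjects use 3 to 5 days and their observed/true ratio is r, the pooled error is r^p − 1. The median shortfall is 17% (r = 0.828); the even-split extremes are 4% and 31% (r = 0.96 and 0.69).

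| p | r = 0.828 | r = 0.96 | r = 0.69 |
|---|---|---|---|
| 0.25 | −4.6% | −1.0% | −8.9% |
| 0.50 | −9.0% | −2.0% | −16.9% |
| 0.75 | −13.2% | −3.0% | −24.3% |

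The error is about 0% if every profiled cycle uses 2 days. The documents do not give p.

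**4. Sample moved to the last infusion.** With the third sample 0.5 h after the last infusion, the Cmax error is under 1% for 2 to 5 days with an even split and under 3% with the front-loaded splits. Baseline-corrected AUC error in 3- to 5-day cycles moves from about −5% to +1% to about +1% to +6%.

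**The case against.** IgPro10 Cmax is descriptive. SAP section 7.3 plans no hypothesis tests, and no model or decision rule uses Cmax. The protocol's stated reason for measuring IgPro10 PK is relative bioavailability, which rests on AUC alone. This limits the consequence, but Cmax remains a named secondary endpoint that will be reported with a confidence interval.

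The split of days and of daily doses is unknown, and front-loading shrinks the error. That is correct, and it is why ranges are given.

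A draw after the 2nd infusion exists in every cycle, so its nominal time aligns across subjects for mean profiles. That is a real benefit, but it comes at the cost of the peak in every longer cycle.

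The true peak also depends on the number of days. In the illustrative case the 3-, 4- and 5-day true peaks are 5%, 9% and 12% below the 2-day peak (73.1, 70.1 and 67.6 against 76.9). Re-timing the sample removes the sampling error, not this difference between regimens. This stands, and it is a further reason to show the number of days beside Cmax.

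tmax is only listed, so it carries little weight. The number of days can be recovered from the infusion listings (protocol 10.4.1), but the PK summaries do not show it, and the IgPro10 exposure summary (SAP 11.1) does not list it. Splitting about 10 subjects per sequence by days would give small groups, which is also true.

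**Conclusion.** The concern holds. The sampling tables, the one-infusion-per-day definition and the observed-maximum rule show that no sample captures the end of dosing in 3- to 5-day cycles. The plan neither adjusts Cmax for cycle length nor reports it by cycle length.

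The size rests on assumed PK values and on the dose split. With an even split the shortfall in total Cmax is 7-22% for 3 days, 6-31% for 4 and 4-31% for 5, against under 1% for 2 days. The effect on the reported mean depends on the unknown share of longer cycles.

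The schedule should be corrected, but the consequence is confined to a descriptive secondary endpoint and a listed time. The primary endpoint is untouched, and the effect on AUC0-tau and %F is small.

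**What to change.** Re-time AP17 and BP6 to 1 to 60 min after the last infusion of the Week 29 or Week 13 cycle. This is a wording change to one existing draw in two tables. It adds no blood sample and changes no dosing, and the subject is already on site because all IgPro10 is given there (protocol 5.1.3.1).

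The cost is that the sample's nominal hour will differ with the number of days, which complicates mean profiles by planned time (SAP 12.1). AUC accuracy does not improve.

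If sampling is already complete, make the change in the SAP:
- report IgPro10 Cmax by number of infusion days in the profiled cycle, accepting small groups;
- show the number of days beside tmax in the listing;
- label Cmax from 3- to 5-day cycles as a lower bound.

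Exclude no subjects, and leave the relative bioavailability analysis as planned.

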CCI		X																		
CCI		X																		
IP assignment		X				X				X				X						
IgPro10 IV infusion ^N		X				X				X				X						
Complete infusion form			X			X				X				X						
Assess and record AEs ^O	X	X		X	X			X	X			X	X			X				X
Record concomitant therapy ^O	X	X		X	X			X	X			X	X			X				X

A = during or after infusion; AE = adverse event; CCI = CCI; CCI = CCI; ECG = electrocardiogram; EOS = End of Study; EOT = End of Treatment; CCI = CCI; IgA = immunoglobulin A; IgG = immunoglobulin G; IP = investigational product; IV = intravenous; CCI = CCI; CCI = CCI; P = before infusion; PFT = pulmonary function test; CCI = CCI; PK = pharmacokinetics; CCI = CCI; CCI = CCI; TEE = thromboembolic event; CCI = CCI; UNS = unscheduled.

Notes to the schedule of assessments:

- A: A visit window of ± 2 days relative to Randomization is applicable to all treatment visits.
- B: At unscheduled visits, any procedure may be performed at the discretion of the investigator.
- C: All assessments should be done before randomization with the exception of infusion and completion of the infusion form.
- D: A full physical exam will be conducted at Screening and Week 1. An abbreviated physical exam will be performed at all other applicable visits.
- E: At the Week 1 Visit, only CCI is to be assessed.
- F: Vital signs to be assessed before, during, and after each IgPro10 infusion
- G: Body weight to be assessed before each IgPro10 infusion.
- H: See Table 1 for specific laboratory tests.
- I: Blood and urine samples for hemolysis testing will be collected at Screening and within 7 to 14 days after each IgPro10 dose.
- J: TEE safety assessments; refer to Section 8.1.1.3 for detailed description.
- K: Renal function assessments (blood chemistry parameters and urine sample). Refer to Section 8.1.1.4.

- L:** Serum for retention and analysis of biomarkers and whole blood for RNA and DNA to be collected. Blood for DNA collected only at Screening. Blood for autoantibodies not collected Week 5.
- M:** Refer to [Pharmacokinetic Schedule of Assessments: Sequence B](#) for full PK sample collection schedules.
- N:** IgPro10 will be administered at the study site over 2 to 5 consecutive days. IgPro10 assignment at UNS visit only if weight change requires dose volume adjustment; changes of > 10% of body weight from baseline / reference visit will require a dose adjustment. IgPro10 infusion at UNS visit only if applicable per dosing schedule.

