3.3 Scientific Rationale

3.3.1 Study Design Rationale

The proposed crossover design with 2 sequences will provide a reliable estimate of IgPro20 relative bioavailability because IgPro20 and IgPro10 treatment differences are measured within a subject rather than between subjects with SSc; both inter- and intra-individual variability will be characterized. This study design will also help to investigate the potential difference in the relative bioavailability of IgPro20 (SCIG) when given before or after IgPro10 (IVIg) in SSc subjects. During both Treatment Period 1 and Treatment Period 2 in each sequence, several PK samples to measure IgG trough concentrations will be collected to assess the steady state of IgPro20 or IgPro10 and carry-over effects on Treatment Period 2 from Treatment Period 1. In addition, PK samples will be frequently collected over the last dose period to fully characterize the PK of IgPro20 and IgPro10, respectively, for each treatment period in this patient population. Specific PK assessments are described in [Section 8.1.2](#).

CCI

The 16 weeks of treatment for both IgPro20 and IgPro10 will allow for the assessment of safety and preliminary efficacy signals as well as assessment of IgPro20 and IgPro10 PK profiles at the steady state. The duration of PK assessments is based on IgG trough

concentrations measured in the pivotal phase 3 study in patients with CIDP (IgPro20_3003 study), indicating that IgPro20 and IgPro10 would reach steady state within approximately 8 weeks. Importantly, several trough concentrations will be determined for IgPro20 and IgPro10 in this study to confirm that steady state is reached before the full PK profile of IgPro20 or IgPro10 is assessed in subjects with SSc.

Not having a washout period between treatments will not impact the full PK characterization, since the full PK profile of IgPro10 in the respective treatment period of each sequence will be obtained at the end of the treatment period, when it is assumed that steady state will be reached. The relative bioavailability of IgPro20 will be evaluated based on the dose-normalized $AUC_{0-\tau}$ of IgPro20 and IgPro10 without the need of a washout interval. Moreover, no washout period between the 2 treatments will shorten the study duration and potentially be less burdensome for SSc subjects.

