	AUC _{0-last} C _{max} t _{max}	AP15 BP4	Last quantifiable time point at or before AP22/BP11

* AH5/BH16= 1 to 60 min before 1st infusion
 AH10/BH21= 168 h (7 days) \pm 10 h after 1st infusion
 AH11/BH22= 240 h (10 days) \pm 10 h after 1st infusion
 AP15/BP4= 1 to 60 min before 1st infusion
 AP22/BP11= 672 h (28 days) \pm 24 h after 1st infusion

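### In Sequence B, a protocol-compliant BP11, which closes the IgPro10 AUC0-tau, can be drawn after IgPro20 has started and so bias the reference AUC slightly upward.

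*Protocol*

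**What the plan says.** **Timing of BP11.** The Sequence B PK schedule sets BP11 at "672 h (28 d) ± 24 h (after 1 st infusion, Week 13"). Note E, attached to BP11, reads: "Sample should be collected at the hour of timepoint (± window) indicated, even if not aligned with indicated week". Note A, attached to the sample drawn right after the first Week 13 infusion (BP5), reads: "Serves as the reference collection for the subsequent follow-up collections".

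**Link to the next period.** BH12 is the Week 17 sample, due "1 to 60 min before 1 st infusion", so it cannot contain IgPro20. Note D covers both samples: "BP11 and BH12 can be taken at the same time point, if appropriate with dosing schedule and visit window".

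**Visit windows.** The notes to both Sequence B schedules state: "A visit window of ± 2 days relative to Randomization is applicable to all treatment visits". Weeks 13 and 17 are thus each tied to randomization, not to one another.

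**No washout.** Protocol section 3.3.1 argues: "Not having a washout period between treatments will not impact the full PK characterization". Its reason is that the full profile is taken at the end of each period, at assumed steady state.

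**Analysis.** SAP section 12.2, Table 9, runs the Sequence B IgPro10 AUC0-tau from BP4 to BP11, with tau of 672 h. Its footnote defines "AP22/BP11= 672 h (28 days") with the same ±24 h. SAP section 7 uses actual sampling times. No sentence says what to do with a BP11 drawn after IgPro20 has begun.

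**The concern.** The Week 13 to Week 17 interval is nominally 28 days, which is also BP11's nominal time. BP11 therefore falls on the changeover between products, and half of its window lies beyond it even on the planned calendar. When Week 13 runs late and Week 17 runs early, a site that follows note E draws BP11 after the first subcutaneous dose.

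Such a sample measures IgPro10 plus newly absorbed IgPro20, but it closes the IgPro10 AUC that forms the denominator of %F. The error has one direction: the reference AUC goes up and %F goes down. It also affects one sequence only. In Sequence A nothing is dosed after the matching sample AP22, and the IgPro20 profiles end with no overlapping infusion. Relative bioavailability is a secondary endpoint, and SAP section 12.3 also estimates it separately by sequence, with about 10 evaluable subjects in each.

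**Working it through.** **1. The plan's own figure.** Week 13 begins on Day 1 + 12×7 = 85 and Week 17 on Day 1 + 16×7 = 113. The gap is 28 d × 24 = 672 h, which matches BP11's nominal time and tau. BP11's window is 648–696 h.

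**2. Range of the gap.** Gap = 28 d + (Week 17 offset − Week 13 offset), each offset from −2 to +2 d. This gives 24–32 d, or 576–768 h.

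**3. Counts over the 25 whole-day offset pairs.**

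| Gap (d) | Pairs | BP11 window relative to IgPro20 start (h) |
|---|---|---|
| 24 | 1 | +72 to +120 |
| 25 | 2 | +48 to +96 |
| 26 | 3 | +24 to +72 |
| 27 | 4 | 0 to +48 |
| 28 | 5 | −24 to +24 |
| 29–32 | 10 | ends at or before the start |

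- Every in-window draw follows IgPro20: 1 + 2 + 3 = **6 of 25**.
- At least part of the window follows IgPro20: 6 + 4 + 5 = **15 of 25**, including the nominal calendar.

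Counting from BP5 (note A) moves BP11 later by the length of the first infusion. For 4–10 mL/kg per day at a constant 1.2–4.8 mL/kg/h that is 4/4.8 = 0.8 h to 10/1.2 = 8.3 h. The counts ignore this shift. The preceding sample, BP10, is due by 504 + 24 = 528 h, before the earliest start at 576 h, so only BP11 is exposed.

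**4. Size.** The documents give no kinetics. Assumptions: one compartment; half-life 21–35 d; SC absorption half-life 24–48 h; F = 0.7; SC sessions of 0.25 g/kg, 72 h apart; four IV cycles of 2 g/kg. Concentrations are per unit volume, which cancels.

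- SC rise at s hours after a session: F × 0.25 × ka/(ka − k) × (e^(−ks) − e^(−ka·s)).
- Worst case: half-life 21 d (k = 0.001375/h), absorption half-life 24 h (ka = 0.02888/h), IgPro20 start at 576 h, BP11 at 696 h, hence s = 120 and 48 h. The multiplier is 0.7 × 0.25 × 1.05 = 0.1838. Rise = 0.1838 × (0.848 − 0.031) + 0.1838 × (0.936 − 0.250) = 0.150 + 0.126 = 0.276.
- IV level at 696 h, each cycle treated as a single dose: 2 × 0.384 × (1 + 0.397 + 0.158 + 0.063) = 1.242. BP11 is 0.276/1.242 = 22% too high.
- Log-trapezoid from 504 h (level 1.617) to 696 h: clean 192 × (1.617 − 1.242)/ln(1.617/1.242) = 272.8; contaminated, with end level 1.518, 300.8. The difference is 28.0. Clean AUC = 2 × 1.617 × (1 − 0.384)/0.001375 = 1,449. Inflation = 28.0/1,449 = **1.9%**.
- Over the full grid (starts 576–672 h, draws 648–696 h, draw after start), BP11 is about 2–22% high and the AUC about **0.2–2%** high.
- Averaged over the 25 pairs with equal weight (an assumption), mean AUC inflation is 0.06–0.14% if BP11 is always drawn at 648 h and 0.14–0.31% at 672 h.

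**5. Effect on %F.** Inflating the denominator by x lowers %F by x/(1 + x), so 2% becomes 0.02/1.02 = 1.96%.

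**6. Limits of BH12 as a substitute.** If IgPro20 starts at 576 h, BH12 is a Day-24 level. Relative to Day 28 it is 2^(4/35) = 1.08 to 2^(4/21) = 1.14, or 8–14% high. The area left to extrapolate is (2^(−24/h) − 2^(−28/h))/(1 − 2^(−28/h)) for half-life h in days: 0.056/0.603 = 9% at 21 d and 0.047/0.426 = 11% at 35 d.

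**The case against.** **Safeguards exist.** SAP Table 2 ends Sequence B Period 1 at the first IgPro20 infusion, and section 12.2 works from profiles in each Treatment Period, so a late BP11 could be called out of period. BP11 is filed under Week 16. Note D shows that the authors saw the changeover, and on the nominal calendar a draw paired with BH12 is clean. The per-protocol sets allow case-by-case exclusion before lock. Some non-compartmental conventions sit in a sponsor guideline that is not available here.

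These points reduce the problem without closing it. Table 9 names BP11 as the end point and does not refer to Table 2. Note E overrides the week label. The main PK analysis uses the safety set, with the per-protocol sets only for sensitivity, and a BP11 that breaks no rule is not an obvious exclusion.

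**The bias is tiny.** This stands. An average of about 0.3% or less in one sequence of about 10 subjects is negligible beside any plausible sampling error.

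**Stronger readings a reader might infer, which the documents do not support:**

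- *Ctrough is contaminated.* The schedule labels only BP2–BP4 as troughs, SAP section 12.2 requires a trough to precede the next infusion, and Table 9 assigns no trough to BP11.
- *Cmax is contaminated.* Table 9's interval does reach BP11, but with a 35-day half-life the Day-28 level is 2^(−28/35) = 0.57 of the peak. Even 22% higher it is 0.57 × 1.22 = 0.70 of the peak.
- *It could pass for a sequence or carry-over effect.* The size is far too small for that.
- *IgPro20 starts before 672 h in 10 of 25 pairs, so 40% are contaminated.* In the four 27-day pairs a draw at 648 h, just before the infusion, is still in window. None of these counts is a frequency.

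**Conclusion.** The gap in the rules is real and its effect is small. The timing follows from the documents alone: a compliant BP11 may follow the first IgPro20 infusion in 15 of 25 whole-day offset pairs and must in 6, and Table 9 would still use it to close the IgPro10 AUC0-tau. Protocol Appendix 4 lets visits move beyond ±2 days with approval, so the real spread may be wider.

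The size rests on assumed kinetics: about 0.2–2% upward bias in an affected subject's reference AUC, less on average, with a near-equal proportional fall in %F, in Sequence B only. A cruder calculation, with an assumed BP11 rise of 1–3 g/L on a mean corrected IgG of 5–15 g/L, gives 84 × 1/(15 × 672) = 0.8% to 84 × 3/(5 × 672) = 7.5%. Its upper end implies a rise of 60% of the mean level, which the superposition does not produce.

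The case for acting is that the bias is avoidable, goes one way, affects one sequence and costs almost nothing to remove. It does not threaten the bioavailability conclusion.

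**What to change.** **PK schedule, Sequence B, note D.** Replace the permission with a requirement: BP11 is drawn before the first IgPro20 infusion, and is combined with BH12 if that infusion falls before BP11 would otherwise be taken. State that this takes precedence over note E.

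**SAP Table 9.** Add a rule: any BP11 taken after the start of IgPro20 is excluded from the IgPro10 parameters; BH12, at its actual time, becomes the last IgPro10 concentration; and where BH12 precedes 672 h, AUC0-672 is completed by log-linear extrapolation from the last clean baseline-corrected samples. Add that an early BH12 is not reported as the 28-day trough, since at 576 h it would read about 8–14% high.

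**Cost.** One footnote and a short SAP rule. BH12 is already scheduled, so there is no new sample or visit, and dosing and visit windows are unchanged. The downside is some extrapolated area in short-gap subjects: at most 96 of 672 h, about 9–11% of the area under the same kinetics. If samples have already been drawn, the SAP rule alone, set before database lock, protects the analysis.
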